9.4 Data sources

The study will be conducted in three databases: the PHARMO Database Network (PHARMO) in The Netherlands, The Health Improvement Network (THIN) in the United Kingdom and the Health Search Database (HSD) in Italy. These databases have also been used in the EMA commissioned study “Patterns and Determinants of Use of Oral Contraceptives in the European Union” (EMA/2001/37/CN). A fact sheet from this study can be found on www.pharmo.com under ‘Partners – EU Collaborations’.

9.4.1 PHARMO Database Network - The Netherlands

The PHARMO Database Network includes several linked databases which contain data on patient demographics, mortality, drug dispensings, hospital morbidity, laboratory, pathology and general practitioner information from more than 4 million inhabitants in defined areas of the Netherlands. The different databases are linked through probabilistic linkage methods. There is a gatekeeper function by the general practitioner (GP) and the GP Database will be best suited to identify diagnoses such as acne and hirsutism. The Out-patient Pharmacy Database will be used as a data source for identification of dispensings of CPA/EE, hormonal contraceptives and acne medication as the GP is not directly involved in refill dispensings. Patient demographics, treatment characteristics and (concomitant) use of hormonal contraceptives will be studied in this population. Diagnoses of acne, hirsutism and other hyperandrogenic conditions are captured in the GP database and therefore previous diagnosis of acne, hirsutism or other hyperandrogenic conditions and previous acne treatment (by presence or absence of acne diagnosis) will be studied in the overlapping population between the Out-patient Pharmacy Database and the GP database. Current size of the overlapping population is ca. 1.1 million.

The PHARMO Database Network has already been used for several studies in the field of hormonal contraceptives. Throughout this report, note that “prescription” refers to “dispensing” for the PHARMO data.

GP database

The General Practitioner (GP) Database comprises data from electronic patient records registered by GPs. The records include information diagnoses and symptoms, laboratory test results, referrals to specialists and healthcare product/drug prescriptions. The prescriptions records include information on type of product, date, strength, dosage regimen, quantity and route of administration. Drug prescriptions are coded according to the WHO Anatomical Therapeutic Chemical (ATC) Classification System (www.whocc.no/atc_ddd_index). Diagnoses and symptoms are coded according to the International Classification of Primary Care (ICPC) (<https://www.nhg.org/themas/artikelen/icpc>), which can be mapped to ICD codes, but can also be entered as free text. GP data cover a catchment area representing 3.2 million residents.

Out-patient Pharmacy Database

The Out-patient Pharmacy Database comprises GP or specialist prescribed healthcare products dispensed by the out-patient pharmacy. The dispensing records include information on type of product, date, strength, dosage regimen, and quantity, route of administration, prescriber specialty and costs. Drug dispensings are coded according to the WHO Anatomical Therapeutic Chemical (ATC)

Classification System (www.whooc.no/atc_ddd_index). Out-patient pharmacy data cover a catchment area representing 4.2 million residents.

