Prior treatment of acne, according to European treatment guidelines², will be assessed in the year prior to the index date (index date – 365 days, excluding index date; for included product names and ATC codes see Table 16.3 and Table 16.4 in Annex 2). Acne treatments will be classified as topicals, systemic preparations and hormonal agents and assessed separately for patients with and without an acne diagnoses in the year prior to index date. Because many of the drugs in the tables are not specific for acne, a pragmatic approach will be taken to select actual acne treatment in the study population: 1) select drugs by ATC or Gemscript code; 2) define dose and route of administration; 3) check with local guidelines for the approved indication of use and only include drugs that are approved for acne (alternative indications may exist). This check with the local guidelines is efficient because only the drugs that are actually used in the study population have to be checked once this data is available. Acne treatments will be further classified to whether it is only approved for acne, or also approved for other indications to allow sensitivity analysis.

Prior diagnoses of hyperandrogenic conditions or medical conditions where EE/progestin combinations are prescribed for frequently will be assessed in the year prior to index date (index date – 365 days, excluding index date; for included codes, see Table 16.5 and Table 16.6):

- Acne
- Alopecia
- Contraceptive management
- Hirsutism
- Menstrual problems
- Oligomenorrhoea/amenorrhoea
- Polycystic ovary syndrome (PCOS)
- Seborrhoea

For the 2017 study extension the following will be assessed:

Demographic characteristics:

- Age at index date (in years, categorized, mean (\pm SD), median (IQR))
- History available prior to the index date (in years, categorized, mean (\pm SD), median (IQR))
- Follow-up available after the index date (in months, categorized, mean (\pm SD), median (IQR))

Concomitant use of hormonal contraceptives:

- Number of CPA/EE treatment episodes (categorized, mean (\pm SD), median (IQR))
- Summed duration of CPA/EE use (in months, categorized, mean (\pm SD), median (IQR))
- Concomitant use of hormonal contraceptives (concomitant, potential concomitant, non-concomitant or no use of hormonal contraceptives)
- Duration of concomitant use of CPA/EE and hormonal contraceptives (≤ 28 days concomitant use, $>28 - 84$ days concomitant use or >84 days concomitant use, mean (\pm SD), median (IQR))

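### PHARMO reports prior acne treatment only in the GP-linked subset, although only the split by acne diagnosis needs GP data; an all-users result would be more precise and would match the denominator of the other PHARMO tables

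*Protocol*

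**What the plan says.** Section 8.1 lists previous acne treatment among the main objectives, and the abstract assesses it in the study population. Neither attaches a diagnosis condition.

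Section 9.4.1 names the data source for PHARMO: "The Out-patient Pharmacy Database will be used as a data source for identification of dispensings of CPA/EE, hormonal contraceptives and acne medication". It then gives the reason for using GP data, "Diagnoses of acne, hirsutism and other hyperandrogenic conditions are captured in the GP database and therefore previous diagnosis of acne", and concludes that "previous acne treatment (by presence or absence of acne diagnosis) will be studied in the overlapping population". Demographics, treatment characteristics and contraceptive use are studied in the pharmacy population.

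On size, the section states "Current size of the overlapping population is ca. 1.1 million", against "Out-patient pharmacy data cover a catchment area representing 4.2 million residents" and "GP data cover a catchment area representing 3.2 million residents".

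Section 9.3 plans acne treatments to be "assessed separately for patients with and without an acne diagnoses in the year prior to index date". It also plans to classify each drug by whether acne is its only approved indication, so that a sensitivity analysis is possible. The shells of Tables 14.5 and 14.6 follow the split: one block for users with an acne diagnosis, one for users without, and none for all users.

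**The concern.** The two diagnosis blocks add up to an overall figure, but in PHARMO only for women with linked GP data. Starters without the link never contribute to any acne-treatment result, although their dispensings are in the designated source and the entry criteria give each of them at least 365 days of recorded history.

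The measure matters. Section 7 records the recommendation that the product be used for acne only after alternatives such as topical or antibiotic treatment have failed. The frequency of such treatment before the index date, and its movement between 2011/2012 and 2014, is what the study can say about that. PHARMO also has a particular strength here: its pharmacy data include specialist as well as GP prescribing, whereas section 9.9 notes that GP databases lack specialist prescriptions.

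At stake are the width of the intervals, chiefly for the small 2014 cohort, and a mismatch of denominators: acne treatment describes linked women, while the other PHARMO treatment tables describe all pharmacy starters. The protocol does not discuss whether the two groups are alike.

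**Working it through.** The protocol states neither a precision target nor the linked share of starters, so there is no figure of its own to reproduce. The share has to be assumed, and two values are shown.

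**Inputs**
- Overlap 1.1 million, pharmacy catchment 4.2 million (section 9.4.1).
- PHARMO starters: 7,876 in 2011, 7,562 in 2012 and 1,401 in 2014 (Table 15.1), read as the pharmacy cohort because section 9.4.1 studies demographics there.
- Preliminary PHARMO count for 2011-2012: 2,700 (section 9.5).

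**Linked share f**
- Assumption A, starters spread like the catchment: f = 1.1/4.2 = 0.262. With the rounder figure of 4 million also given in section 9.4.1, f = 1.1/4.0 = 0.275.
- Assumption B, the 2,700 are the linked starters: f = 2,700/(7,876 + 7,562) = 2,700/15,438 = 0.175. The protocol does not say that they are. The sum of the two calendar years may also count a few women twice.

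**Base sizes (n × f)**

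| Year | All starters | A (26.2%) | B (17.5%) |
|---|---|---|---|
| 2011 | 7,876 | 2,063 | 1,377 |
| 2012 | 7,562 | 1,981 | 1,323 |
| 2014 | 1,401 | 367 | 245 |

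**95% half-width for 2014**, 1.96 × √(p(1−p)/n), in percentage points

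| p | All starters | A | B |
|---|---|---|---|
| 0.1 | 1.6 | 3.1 | 3.8 |
| 0.3 | 2.4 | 4.7 | 5.7 |
| 0.5 | 2.6 | 5.1 | 6.3 |

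**95% half-width for the 2012-2014 difference**, 1.96 × √(p(1−p)(1/n₁ + 1/n₂)), at p = 0.5
- All starters: 0.98 × √(1/7,562 + 1/1,401) = 2.85 points.
- A: 0.98 × √(1/1,981 + 1/367) = 5.6 points.
- B: 0.98 × √(1/1,323 + 1/245) = 6.8 points.

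Whatever p is, restricting to a share f widens an interval by 1/√f, which is 1.95 under A and 2.39 under B. For 2011 and 2012 the half-width at p = 0.5 is 1.1 points in all starters and 2.2 under A, so the practical effect is mainly in 2014.

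**The case against.** The strongest reply is that the restriction is reasoned and consistent. Sections 9.3 and 9.4.1 and the table shells all describe an analysis by acne diagnosis. That analysis cannot be done without GP data, so nothing usable for it is lost. This stands. A reader might infer that three quarters of the PHARMO data are thrown away without reason. The documents do not support that: a reason is given, it is sound for the stratified rows, and the three-quarters figure is a share of catchment population, not of starters.

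Second, the split has a purpose. Prior treatment among women with acne is the more informative figure. Several listed classes, including oral antibiotics and hormonal contraceptives, are not specific to acne, so an all-users percentage mixes indications and could move over time with the indication mix. This also stands, and it shapes the fix. It carries less weight for drugs approved only for acne, which section 9.3 already plans to identify. Section 9.9 itself warns that under-recorded diagnoses limit the assignment of indication.

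Third, an all-users row adds nothing in THIN or HSD, where the two blocks already sum to everyone. That is correct, so the point is confined to PHARMO.

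Fourth, the 2011, 2012 and 2014 runs appear to have been carried out: Table 15.1 already shows their counts, and their final report was planned for March 2016. The 2015-2017 extension does not assess acne treatment. So the change would supplement earlier reporting and would not alter the extension.

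Finally, the study is descriptive, and a half-width of 5 to 6 points is not shown to change a conclusion. That limits the weight of the point but does not remove it.

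**Conclusion.** The point holds as one of efficiency and coverage. The objective is unconditional and the dispensings exist for all pharmacy starters, yet every PHARMO acne-treatment result comes from the GP overlap. The stated reason covers the stratified rows only.

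On the catchment assumption, intervals for the overall PHARMO figure are about twice as wide as they need be; on the less certain reading of the section 9.5 count, about 2.4 times. Both linked shares are assumptions, and the overlap is given at its current size, not for the study years.

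Two stronger readings should be avoided. A reader might infer that the protocol contradicts itself; it does not, since the restriction is stated openly and carried through consistently. A reader might also infer that the linked-subset results are biased. That would require linked and unlinked women to differ, and nothing in the protocol shows that they do. The diagnosis-specific rows could not be enlarged in any case. The point concerns the 2011/2012 and 2014 runs only.

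**What to change.** In section 9.4.1 and Tables 14.5 and 14.6, add for PHARMO an *All users* block based on all pharmacy starters. Within it, show drugs approved only for acne separately from drugs with other indications, using the classification already planned in section 9.3. State both denominators, all pharmacy starters and the GP-linked subset. Leave the split by acne diagnosis in the GP-linked subset unchanged. THIN and HSD need no change.

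No new data source is needed, because the dispensings come from the database already designated for them. If the earlier runs have been reported, the block would be a supplement to that report. The cost is one extra table block, plus a note that the non-specific classes must be read with caution because the indication is unknown outside the GP link.

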9.4.2 The Health Improvement Network (THIN) – United Kingdom

The Health Improvement Network (THIN) database is a longitudinal, primary care database that contains diagnostic and prescribing information recorded by the GPs as part of their routine medical practice. General practitioners are gatekeepers in the UK national health system and in THIN data on ca. 4 million active patients are captured.

In general there is a good coverage of OC prescriptions in THIN (some exceptions exist, e.g. prescriptions from family planning clinics are not recorded), although, in the UK, general practice is cited as the most common provider of contraceptives for women³. The database has already been used for drug utilization studies on contraceptive methods^{4,7}. In the UK, contraceptives have been provided free of prescription charges since 1974, and continuation rates and switching patterns are unlikely to be influenced by the costs of the individual contraceptives and the required logistics for refilling prescriptions. Ambulatory diagnosis such as acne, hirsutism and polycystic ovary syndrome (PCOS) would generally be recorded and coded by the GP, as well as acne treatments, as long as they are prescription drugs. The use of primary care databases such as THIN is a well-accepted method for examining drug use in broad patient populations.

9.4.3 Health Search Database (HSD) - Italy

The Health Search/Longitudinal Patients Database (HSD) is a primary care database that was established in 1998 by the Italian College of General Practitioners. It contains data from computer-based patient records of more than 800 GPs from all Italian regions, covering a population of ca. 1.3 million active patients. The GPs voluntarily agreed to collect data and after attending training have to use specifically designed software to record data during their normal daily clinical practice. The database includes information on patient demographics, GP registration information, drug prescriptions, diagnoses, tests and test results and date of death. In general, hormonal contraceptive prescriptions are reliably recorded in HSD and the database was part of the EMA commissioned study “Patterns and Determinants of Use of Oral Contraceptives in the European Union” (EMA/2001/37/CN). Diagnosis such as acne, hirsutism and polycystic ovary syndrome (PCOS) would generally be recorded and coded by the GP, as well as acne treatments, as long as they are prescription drugs. With regard to capture of hormonal contraceptive use, it is acknowledged that the data is not exhaustively captured in the database. The underestimation is mainly due to private prescriptions. HSD is the only data source to have part of private prescription (claims database do not have it at all) and, given that the indication of drug use is relevant for this protocol, HS is the only data source to possess it in Italy.

9.5 Study Size

In a preliminary analysis of 2011-2012 about 9,000 new users of CPA/CEE were observed across the databases: 2,700 new users in PHARMO, 5,600 new users in THIN and 700 new users were observed in HSD.

9.6 Data management

9.6.1 PHARMO Database Network - The Netherlands

The PHARMO Database Network combines data from different healthcare databases (pharmacy, hospital, GP etc.). These different databases are probabilistically linked through validated algorithms that do not invade the privacy of the patients. Before linkage of the different databases, patients for whom crucial information needed for linkage is missing (date of birth, gender, GP) are removed.

Healthcare databases are used as administration tools in patient care and have their limitations with regard to their use in scientific research. For example, the completeness of data may differ per healthcare centre. Therefore, with each update of the database the completeness of registration per healthcare centre is evaluated (overall and within specific care areas, number of records, internal consistency and comparison of calendar years).

For each study, specific study checks on the linked data are performed. These partially depend on which specific databases are required for the study and their importance to the selection of patients or outcomes. For each database it is determined per patient from which time point onwards the patient is registered in the specific database and from which time point the patient is lost to follow-up (due to for example death or moving out of the PHARMO catchment area). Patients are regarded eligible to be included in a study if they are registered and can be followed in all required databases.

Study data are manipulated and analysed using the utility SAS Enterprise Guide, an environment for SAS enabling the storage of syntaxes or codes belonging to a single study in one project file, subdivided into project flows for different aspects of a study.

9.6.2 The Health Improvement Network (THIN) – United Kingdom

The Health Improvement Network (THIN) is a collaboration between two companies, In Practice Systems Ltd. (INPS), developer of Vision software used by GPs in the UK, and EPIC, provider of access to data for use in medical research. THIN data are collected during routine practice and regularly delivered to THIN. THIN data collection started in 2003, currently contains the electronic medical records of almost 8 million patients (more than 3 million active patients) collected from over 386 general practices in the UK covering more than 5.7% of the population in the UK⁸. Patient data are arranged in four standardized (Patient, Medical, Therapy and Additional Health Data and one linked (postcode variable indicators) files per practice. Further information is possible to obtain via the Additional Information Service (AIS) including: questionnaires completed anonymously by the patient or GP, copies of patient-based correspondence, a specified intervention (e.g. a laboratory test to confirm diagnosis) and death certificates

9.6.3 Health Search Database (HSD) - Italy

HSD contains information recorded by GPs only. Patients' demographic details are linked through the use of an encrypted code with clinical records (diagnoses, referrals, and tests results), drug prescriptions (drug name, date of filled prescription, and number of days' supply), prevention records, hospital admissions, and date of death. Free-text files are also available.

To be considered for participation in epidemiological studies, GPs should meet "up-to-standard" quality criteria pertaining to the levels of coding, prevalence of well-known diseases, mortality rates, and years of recording. The "data quality" checking is performed every semester.

Study data can be manipulated and analysed using SQL, Stata or SAS syntaxes.

9.7 Data analysis

Patient, treatment and diagnosis characteristics will be reported descriptively. Categorical data will be presented as counts (n) and proportions (%). Continuous data will be presented as means with standard deviation (SD) and as medians with inter quartile range (IQR) when appropriate. Results will be stratified by year of index date. Table shells are presented in Annexes 1 and 2 (sections 14 and 15).

9.8 Quality control

Standard operating procedures at each research centre will be used to guide the conduct of the study. These procedures include internal quality audits, rules for secure and confidential data storage, methods to maintain and archive project documents, quality control procedures for programming, standards for writing analysis plans, and requirements for senior scientific review.

All programming written by the executing researcher will be reviewed independently by a senior researcher. All key study documents, such as the statistical analysis plan and study reports, will undergo quality control and senior scientific review.

9.9 Limitations of the research methods

Drug utilization studies conducted in automated healthcare databases allow identification of patients who are prescribed or dispensed the drugs of interest and characterisation of these patients according to prior medical history, use of medications, and patterns of use of medications. Healthcare databases have become a useful tool for conducting research to study the safety of drugs as information on diagnoses and treatments is recorded on an ongoing basis.

Limitations regarding treatment

Healthcare databases are used as administration tools in patient care and have their limitations with regard to their use in scientific research, mainly related to the type and completeness of the recorded information. Regarding treatment data, databases provide detailed information on prescribed and/or dispensed medications but not on the actual use of the medications by patients. Thus, patients may be classified as exposed when they are not actually taking the drug. Furthermore, databases often do not record the intended duration of use of each prescription (days of supply). This needs to be estimated from the interval between consecutive prescriptions and can result in misclassification of drug exposure. In particular the use of long-acting hormonal contraceptives (intra-uterine devices, injections and implants) may be misclassified. To be eligible for inclusion in our study, women were requested to have at least one year enrolled with the general practitioner, this eligibility criterion may result into some misclassification of exposure of these devices in both directions, potential for false negatives (underecorded use (earlier the year prior index date) or false positivies (removal or ended life cycle of these devices at the time of index date or during the year after). However, we expect the use of LARC to be low in this population, as women initiating CPA are expected to be on average 20-23 years old⁷. As the indication of use is not recorded for most of the prescriptions, the identification of the indication depends on concomitantly recorded diagnoses. Another limitation of the assessment of medication use from databases is that over-the-counter medications are usually not recorded. As OTC medications do play an important role in the treatment of acne the limitation of not recording those needs to be taken into consideration when interpreting the results. Furthermore, as discussed in

the context of information on prescriber (section 9.3), in GP databases only GP prescriptions are recorded, not specialist prescriptions, e.g. from gynaecologists. Completeness of recording of refill dispensings in the GP (prescription) database varies by database.

Limitations regarding diagnoses

Databases of electronic medical records are restricted to information recorded to serve the purpose of the database: primary care, claims, etc. Because these databases were not designed to perform research, underreporting of events may occur. As mentioned in the previous section, this underreporting may limit the assignment of indication of use. In addition, it should be noted that the actual indication may have changed, e.g. in the case of CPA/CEE, some users may have started with the indication acne, but continue after some time because of the contraceptive effect.

